#### 6.4 Patient treatment

All pasireotide LAR injections must be administered only by a medical staff or healthcare professional at each site. Any dose change must be recorded in the Dose Administration Record eCRF. The drug ampoule(s) must be retained for later evaluation by the monitor.

#### **Screening**

On Visit 1, no pasireotide LAR will be given to the patient.

#### **Main Phase Treatment**

The first pasireotide LAR 60 mg IM dose will be administered on Visit 2, after all baseline evaluations are completed and the eligibility to participate in the study is confirmed. Pasireotide LAR will be administered as a depot intragluteal IM injection.

Pasireotide LAR 60 mg IM will be administered by the site staff every 28 ( $\pm$  3) days throughout the Main Phase treatment period (all patients are expected to receive 6 doses of pasireotide LAR every 4 weeks). A dose decrease to 40 mg will be allowed for safety reasons.

#### **End of Study (EOS) Visit**

After the Main Phase of the study (first 24 weeks of treatment), patients benefiting from pasireotide LAR treatment will be offered the opportunity to continue to receive pasireotide LAR, based on the physician's evaluation and the patient's wishes.

Patients who participate in the Extension Phase will be treated with pasireotide LAR for up to 92 weeks or approximately 2 years (Table 7-2), or until pasireotide or other effective therapy becomes commercially available, or until clinical benefit is no longer seen (whichever occurs first).

#### **Extension Phase**

Patients enrolled in the Extension Phase will receive pasireotide LAR IM at Visit 10 and will have the first extension study visit scheduled, which will occur 28 ( $\pm$  3) days after Visit 10. Treatment with pasireotide LAR will be administered by the site's healthcare professional staff every 28 ( $\pm$  3) days, during the Extension Period (see Table 7-2).

Additional Information on the Extension Phase:

The dose will continue to be 60 mg. If a patient is receiving 40 mg due to tolerability issues and such issues are resolved, there may be a dose escalation to 60 mg, at the physician's discretion. If the adverse event reoccur, the dose will be decreased to 40 mg and will be mantained until completion of the Extension Phase or until study discontinuation.

#### Safety Follow-up

All patients in the main and extension phases will be followed for safety for approximately 56  $(\pm 3)$  days after administration of their last dose of pasireotide LAR.

#### 6.4.1 Follow-up for dose-limiting toxicities

Patients whose treatment is interrupted or permanently discontinued due to an AE or abnormal laboratory value must be followed up at least once a week for 4 weeks, and in 4-week intervals thereafter, until resolution or stabilization of the event, whichever occurs first. All patients will be followed up for AEs and serious adverse events (SAEs) for 8 weeks after administration of the last dose of pasireotide LAR (refer to Section 6.4.4 for information on the discontinuation of the study drug).

# 6.4.2 Allowed study drug adjustments

For patients who cannot tolerate the administration schedule specified in the protocol, dose adjustments are allowed so that the patient may continue to receive the study drug.

The study drug for this study will be pasireotide LAR 60 mg given every  $28 \pm 3$  days for 6 months, during the main study period. In case of tolerability issues (see Table 6-2), the pasireotide LAR dose may be decreased to 40 mg in the next scheduled injection. However, patients unable to tolerate the minimum dose of 40 mg will be discontinued from the study.

All dose changes must be recorded in the Dose Administration Record eCRF.

During the Extension Phase, if a patient receives 40 mg due to tolerability issues and such issues are resolved, there may be a dose escalation to 60 mg, at the physician's discretion. If the adverse event reoccurs, the dose will be decreased to 40 mg and the patient will maintain this dose.

Table 6-2 Guideline for treatment of patients experiencing adverse events

Adverse event	Action
CTC Grade ≤ 2 AEs	No drug adjustment
CTC Grade ≥ 3 AEs evaluated as related to the study drug	Decrease intramuscular pasireotide LAR dose to 40 mg.
	If the AE does not improve to grade ≤ 2 with the 40 mg dose, the patient will be withdrawn.

The guidance above must be used for all AEs, except for changes in blood glucose and QTc and for liver safety monitoring. Blood glucose changes must be followed as described on Section 7.5.2.1. Changes in QTc interval must be followed as described on Section 7.5.2.2. Refer to Section 7.5.2.3 for liver safety monitoring.

#### 6.4.3 Other concurrent medication

The investigator must instruct patients to notify the study site about any new medication administered after starting the study drug. All medications (except the study drug) and significant non-drug therapies (including physical therapy and blood transfusions) administered after the patient starts treatment with the study drug must be mentioned in the Concurrent Medication / Significant non-drug therapy eCRF after the study drug is started. If possible, there may be no changes in any concurrent medication during the study until all EOS evaluations are completed.

The use of anticoagulant medication should be avoided.

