#### 5.2 Exclusion criteria

- 1. Patients requiring surgical intervention for relief of any sign or symptom related to tumor compression.
- 2. Previous pituitary surgery.
- 3. Previous medical treatment for pituitary tumor.
- 4. Patients who received pituitary radiation within 10 years before the enrollment visit (Visit 2).
- 5. Prolactin (PRL) levels > 100 ng/mL. (PRL evaluation must be performed with diluted samples in order to ensure prevention of the "hook effect").
- 6. Patients with optic chiasm compression, causing clinically significant acute visual field defects.
- 7. Diabetic patients whose blood glucose is poorly controlled, as proven by HbA1C > 8%. Patients with known history of fasting glucose impairment or diabetes mellitus with HbA1c < 8% may be enrolled; however, blood glucose and antidiabetic treatment must be closely monitored throughout the study and adjusted as required.
- 8. Patients with known gallbladder or bile duct disease, or acute or chronic pancreatitis (patients with asymptomatic colelithiasis and asymptomatic dilation of the bile duct may be enrolled).
- 9. Patients with abnormal coagulation (increased PT or APTT 30% above normal limits) or patients who have received antiacoagulants that affect PT (prothrombin time) or APTT (activated partial thromboplastin time).
- 10. Patients with congestive heart failure (NYHA Class III or IV), unstable angina, persistent ventricular tachycardia, ventricular fibrillation, advanced cardiac block, or history of acute myocardial infarction within 24 weeks before the enrollment visit (Visit 2).
- 11. Screening (Visit 1) or baseline (pre-dose, Visit 2) QTcF > 450 msec.
- 12. Patients with history of syncope or family history of idiopathic sudden death.

- 13. Patients with persistent or clinically significant cardiac arrhythmias.
- 14. Patients with Torsades de Pointes risk factors, such as uncorrected hypocalemia, uncorrected hypomagnesemia, heart failure, clinically significant / symptomatic bradycardia, or high degree AV block.
- 15. Patients with concurrent disease(s) that might prolong the QT interval, such as autonomous neuropathy (caused by diabetes or Parkinson's disease), HIV, cirrhosis, uncontrolled hypothyroidism, or heart failure.
- 16. Patients on medication(s) known to prolong the QT interval.

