## 6.4.4 Discontinuation of the study drug

Patients experiencing unacceptable toxicity (grade  $\geq 3$  AE, including grade  $\geq 3$  changes in laboratory values) that the investigator considers as directly ascribable to the study drugs must have their doses decreased (Section 6.4.2) or be withdrawn from the study.

- Patients who permanently discontinue the study drug between Visit 2 and Visit 9 (inclusive) must be scheduled for the End of (Main) Study Visit (Visit 10) 28 ± 3 days after administration of the last dose of the study medication, when all evaluations listed will be performed. The Safety Follow-up Visit (Visit 11) will be performed approximately 56 ± 3 days after administration of the last dose of study medication.
- Patients who permanently discontinue the study drug in the Extension Phase must be scheduled for the End of (Extension) Study Visit 28 ± 3 days after administration of the last dose of the study medication, when all evaluations listed will be performed. The safety follow-up visit for the extension phase will be performed approximately 56 ± 3 days after administration of the last dose of the study medicaiton.

Patients who discontinue the study drug must be considered as withdrawn from the study after the EOS / Safety Follow-up evaluations are performed or when it's evident that the patient will not return for the EOS evaluations.

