- 11. Previous and concurrent medications comprise any therapy, including chemotherapy, radiation therapy, and surgery, or medication previously received, or ongoing treatment.
- 12. All medications / therapies used to treat tumor or symptoms in this study, given to a patient in a ≤ 4 week period after administration of the last dose of the study treatment, must be recorded in the eCRF. All patients will be followed up for safety for 56 days after administration of the last dose of the study drug.
- 13. Safety follow-up must be performed 56 ± 3 days after the patient has received the last pasireotide LAR dose. For patients who continue in the extension study, this visit will not be performed after the end of the main study, but 56 ± 3 days after the patient has completed the extension study.
- 14. The ECG will be performed before administration of the drug. On Visit 3 (Day 20) and on Visit 6 (Day 76), the ECG will be performed regardless of drug administration.

<del>15.</del> .

- 15. The window to perform gallbladder MRI and US [ultrasound] must not be more than 7 days prior to the scheduled visit.
- 16. If a patient is not assigned to the Extension Phase, the follow-up visit will be Visit 11.

Table 7-2 Visits and evaluations schedule for the Extension Study

Table 1-2 VISI	is and	Cvan	autio	113 30	)110u	u	JI (111	LAL	CHOI	J O	uuy										
Visit	10 	11	12	402	13	14	15	16	17	18	19	20	21	22	23	24	25	26	27	28	29
																				EOS	Follow-up 9
Week	24	28	32	35	36	40	44	48	52	56	60	64	68	72	76	80	84	88	92	96	Last dose + 8
																					weeks
Day	168	196	224	244	252	280	308	336	364	392	420	448	476	504	532	560	588	616	644	672	700
Injection	7	8	9		10	11	12	13	14	15	16	17	18	19	20	21	22	23	24		
Adverse events (DB)	Х	Х	Х	Х	Х	Х	Х	Х	Х	Х	Х	Х	Х	Х	Х	Х	Х	Х	Х	Х	X
Current medical	Х				Х			Х			Х			х			Х			Х	х
conditions (DB)					^			^			^			^			^			^	
Vital signs (DB)	Χ				X			Х			Х			Х			Х			Х	Х
Physical examination (SD)	Х				X			Х			X			Х			Х			Х	Х
Weight (DB)	Х				Х			Х			Х			Х			Х			Х	Х
Pituitary / Sella turcica	Х							Х						х						Х	
MRI								^													
Alpha subunit 	Х							Х						Х						Х	
ECG (DB)	Х				Х			X			Х			X			Х			X	
Gallbladder ultrasound	Х							Х												x	
(DB)	^							^												_ ^	
ECOG Performance status	X				Х			Х			Х			Х			Х			Х	х
(DB)	^				^			^			^			^			^			_ ^	^
Evaluation of symptoms /																					
Disease-related	Х				Х			Х			Х			X			Х			X	
symptoms (DB)																					

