#### 7.3 Treatments

The study medication administered during the study must be documented in the Dose Administration eCRF. Date and time of dose administration will be recorded in the Dose Administration Record. Compliance will be evaluated by the investigator and/or study staff on all visits. Records of study drug used, treatment administered, and intervals between visits will be kept throughout the study. Drug accountability will be registered by the field monitor during site visits and upon completion of the study.

All drugs, including over-the-counter drugs and previous therapies for the disease, taken before administration of the study drug and continuing throughout this study must be documented in the Previous / Concurrent Medication eCRF.

In the Main Phase, patients will receive the study drug on Visit 2 (Day 0) and then every 4 weeks ( $28 \pm 3$  days) thereafter, i.e., on Weeks 4, 8, 12, 16, 20. Patients who enter the Extension Phase will receive the study drug starting on Week 24, and then every 4 weeks ( $28 \pm 3$  days) thereafter, until Week 92.

All therapies administered to a patient within 4 weeks after administration of the last dose of the study medication must be documented in the Therapy Since Discontinuation eCRF.

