5.4.3 Handling of missing values/censoring/discontinuations

A patient whose tumor volume assessment at baseline (Visit 1) is missing will not be considered for the efficacy assessments. Only those patients will be considered for analysis for which baseline and at least one post baseline records are reflecting non missing values. All the analysis will be performed with as observed data i.e. the primary analysis (Week 24) will be based on only patients that have both baseline and Week 24 tumor volume assessment.

The analysis of the primary endpoint will be based on observed cases since the patients population is naive (including not having any surgery) and it is expected that 24 weeks of treatment is needed before meaningful effect are assessed.

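### A tumour volume measured after non-study tumour therapy, most plainly surgery before the Visit 10 MRI, can be scored as response to pasireotide because the response rule sets no condition on such therapy

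*Protocol*

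**What the plan says.** **Entry.** Inclusion 3 requires no previous treatment for the adenoma. Exclusions 2 to 4 cover earlier surgery, earlier drug treatment ("Previous medical treatment for pituitary tumor") and radiation within the preceding 10 years. All look backward from enrolment.

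**On study.** Protocol 6.4.3 asks: "If possible, there may be no changes in any concurrent medication during the study until all EOS evaluations are completed". The one class it names is in the next sentence: "The use of anticoagulant medication should be avoided". Section 6.4.5.1 does not list the start of another tumour therapy among its reasons for withdrawal.

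**What is recorded.** Table 7-1 note 11 defines the data collected: "Previous and concurrent medications comprise any therapy, including chemotherapy, radiation therapy, and surgery, or medication previously received, or ongoing treatment". Section 7.3 adds: "All therapies administered to a patient within 4 weeks after administration of the last dose of the study medication must be documented". These therapies go to their own page ("must be documented in the Therapy Since Discontinuation eCRF").

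**The last scan.** Visit 10 includes the pituitary MRI. Under Protocol 6.4.4, patients who stop the drug early "must be scheduled for the End of (Main) Study Visit (Visit 10) 28 ± 3 days after administration of the last dose".

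**Scoring.** Response is a volume decrease of at least 20% from baseline. SAP 5.4.3 says that "the primary analysis (Week 24) will be based on only patients that have both baseline and Week 24 tumor volume assessment". SAP 5.4.4 adds LOCF as a sensitivity analysis for missing Week 24 values. The footnotes to SAP Tables 7, 8 and B 4 define response by volume alone.

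**The concern.** With no control arm, the response rate supports the drug only if the shrinkage is due to the drug. Pituitary surgery reduces volume directly, and Protocol 1.1 calls it the treatment of choice. Patients doing badly, through visual loss or confirmed growth, are those who leave treatment and may be operated on soon afterwards. If the next MRI is scored without regard to the operation, a treatment failure becomes a treatment success, and the error favours the drug. The same unconditioned rule feeds LOCF, time to response, the volume-change summaries and the extension-phase rows on sustained response. The trial collects the information needed to recognise these cases, but no analysis uses it.

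**Working it through.** **Step 1. Does the plan's own arithmetic reproduce?** Protocol 10.6 and SAP 5.6 take n = 19 and a binomial count X.

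- P(X ≥ 2) = 1 − (1−p)^19 − 19p(1−p)^18.
- At p = 0.10: 1 − 0.1351 − 0.2852 = 58.0%, as stated.
- At p = 0.05: 1 − 0.3774 − 0.3774 = 24.5%, stated as 25%.
- The exact (Clopper–Pearson) 90% interval for 2/19 is 1.9–29.6%, as tabulated.

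The gap is therefore in the endpoint rule. The arithmetic is sound.

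**Step 2. Which scans can be affected?**

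| Situation | Timing | Primary observed-case analysis | LOCF |
|---|---|---|---|
| Injection 6 given, surgery, Visit 10 on schedule | Day 140 to Day 168 = 28 days | Counted as response | Not used; Week 24 is observed |
| Early stop, surgery, early Visit 10 treated as V10 | About 28 days after last dose | Counted as response | Not used |
| Same patient, strict Week 24 reading | Same | Left out; Week 24 is missing | Carried forward as response |

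The first row does not depend on how early stoppers are labelled. The second and third are alternatives: LOCF fills only missing Week 24 values, so one scan cannot enter by both routes. The plan does not say which applies, and SAP Table 7 tabulates by V10.

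**Step 3. What would one case do to the estimate?** The documents give no rate of on-study tumour therapy, so k, the number of such patients among 19, is an assumption (0, 1 or 2). With one other responder and k = 1:

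- scored as non-response: 1/19 = 5.3%, exact 90% CI 0.3–22.6%;
- scored as response: 2/19 = 10.5%, exact 90% CI 1.9–29.6%.

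**Step 4. What would it do to the chance of two or more responders?** If k = 1 and that patient is scored as a responder, one more is needed from 18: 1 − (1−p)^18. If scored as a non-responder, two are needed from 18: 1 − (1−p)^18 − 18p(1−p)^17.

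| True rate | k = 0 | k = 1, scored response | k = 1, scored non-response |
|---|---|---|---|
| 5% | 24.5% | 1 − 0.3972 = 60.3% | 1 − 0.3972 − 0.3763 = 22.6% |
| 10% | 58.0% | 1 − 0.1501 = 85.0% | 1 − 0.1501 − 0.3002 = 55.0% |

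With k = 2 scored as responses, two responders are certain.

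The k = 1 columns are conditional on a case existing. If the chance of exactly one case were 10% and otherwise there were none (an illustration), the figure at a true rate of 5% under the present rule would be 0.9 × 24.5% + 0.1 × 60.3% = 28.1%.

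**The case against.** The best case against is that the event is discouraged, visible and perhaps absent. Section 6.4.3 covers the period up to the end-of-study evaluations, and through the definition in Table 7-1 note 11 its request can be read to reach surgery. Patients needing surgery for compression are excluded at entry. Protocol violation and investigator discretion are grounds for withdrawal, and Protocol 9.3 has breaches identified before lock. All of this stands as mitigation. None of it removes a scan from the analysis. The synopsis mentions a per-protocol repeat, but Protocol 10.1 and SAP 5.1 do not define that set, so it gives no dependable protection.

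A reader might infer more than the documents support:

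- **That cabergoline would produce false responders in the last 4 weeks.** Protocol Table 1-3 shows a decrease in 56% and 54% of patients in two cabergoline series, but after 12 months and without the degree of decrease. A third series shows 0% with quinagolide followed by cabergoline. In Table 1-4, six of seven octreotide series show 0–5% with a decrease; the other shows 43% of 7 evaluable patients. Nothing there shows a 20% fall within about 4 weeks. Drugs started earlier on study fall in the same gap, but surgery is the clear case.
- **That the protocol expects tumour therapy after the last dose.** Section 7.3 and Table 7-1 note 12 require it to be recorded, which is not the same.
- **That two responders or 10% is a pass mark.** The plan calls a rate of at least 10% clinically significant, but it sets no test or success criterion and chose n without regard to power. Both intervals in Step 3 contain 10%.

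**Conclusion.** The gap is real: as written, the response rule counts a qualifying volume whatever other tumour therapy preceded it. For surgery between injection 6 and an on-schedule Visit 10 MRI, the stated rule gives the wrong attribution in the primary analysis. For an early stopper, the misattribution falls in either the primary or the LOCF analysis, depending on an unstated labelling choice.

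The size is conditional. One case among 19 could move 5.3% to 10.5%, with widely overlapping intervals. The rise from 24.5% to 60.3% in Step 4 assumes that one such patient exists, so it should not be read as the expected error of the trial. The frequency is unknown and zero is possible. The change is still worth making before database lock, because n is small, the direction favours the drug, and a decision made after seeing the case would be hard to defend.

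**What to change.** This is a change to analysis wording only; whether such therapy should be permitted is a clinical question outside this point. In SAP 5.4.2–5.4.4, with matching text in 5.5.1 and the footnotes to Tables 7, 8 and B 4, state that:

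- for responder endpoints at a given visit, a volume measured after the start of non-study tumour-directed therapy (surgery, radiotherapy, dopamine agonist, other somatostatin analogue) counts as non-response and is not an LOCF source;
- time to response is censored at the last scan before that therapy, unless response was already reached;
- volume-change summaries are shown without post-therapy volumes, and the affected patients are listed.

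SAP 5.4.4 should also say whether an earlier, pre-therapy scan may be carried forward in place of the excluded one. Identify cases by date from the Concurrent Medication and Therapy Since Discontinuation eCRFs before database lock.

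**Cost.** No new data are needed, and results do not change if no case occurs. The response rate may be slightly lower. A patient who shrank on the drug and then had elective surgery before Week 24 becomes a Week 24 non-responder. This matters because pre-surgical use is part of the study rationale, although a response seen at Week 4 or 12 stays visible in those results and in time to response. Leaving volumes out of the change summaries is informative, which is why the affected patients should be listed.

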## 6.4.4 Discontinuation of the study drug

Patients experiencing unacceptable toxicity (grade  $\geq 3$  AE, including grade  $\geq 3$  changes in laboratory values) that the investigator considers as directly ascribable to the study drugs must have their doses decreased (Section 6.4.2) or be withdrawn from the study.

- Patients who permanently discontinue the study drug between Visit 2 and Visit 9 (inclusive) must be scheduled for the End of (Main) Study Visit (Visit 10) 28 ± 3 days after administration of the last dose of the study medication, when all evaluations listed will be performed. The Safety Follow-up Visit (Visit 11) will be performed approximately 56 ± 3 days after administration of the last dose of study medication.
- Patients who permanently discontinue the study drug in the Extension Phase must be scheduled for the End of (Extension) Study Visit 28 ± 3 days after administration of the last dose of the study medication, when all evaluations listed will be performed. The safety follow-up visit for the extension phase will be performed approximately 56 ± 3 days after administration of the last dose of the study medicaiton.

Patients who discontinue the study drug must be considered as withdrawn from the study after the EOS / Safety Follow-up evaluations are performed or when it's evident that the patient will not return for the EOS evaluations.

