#### 7.5.2 Special Safety

#### 7.5.2.1 Changes in blood glucose

The principal investigator must instruct patients about signs and symptoms of hyperglycemia, and evaluate the risks of hyperglycemia in all patients. It is recommended to follow the guidelines established by international associations specialized in diabetes, such as the American Diabetes Association (ADA) and the European Association for the Study of Diabetes (EASD) (Nathan 2009).

Patients with history or recent diagnosis of fasting glucose impairment, glucose tolerability impairment, diabetes mellitus, or at risk of developing these conditions must monitor blood glucose by means of a fingerstick capillary glucose test twice a day (fasting and 2 hours post-prandial). It is recommended that patients be encouraged to keep a blood glucose diary for appropriate disease management throughout the study, as well as to show the data collected to the physician / diabetes expert for evaluation. The data will not be collected by the sponsor.

It is advised that any patient experiencing fasting plasma glucose > 130 mg/dL (7.2 mmol/L), or 2-hour post-prandial capillary glucose (PPG)  $\geq$  180 mg/dL (10 mmol/L) in two consecutive measurements with an interval of approximately 14 days and/or HbA1c > 7% be evaluated by an diabetes expert for proper treatment (Position statement ADA 2010). Additionally, these patients must be informed on diabetes control. The start or adjustment of anti-hyperglycemic treatment must be considered as soon as possible, at the discretion of the diabetes expert. Additionally, these patients must start blood glucose monitoring by fingerstick capillary glucose test twice a day (fasting and 2 hour post-prandial) if it has not yet been performed. It is recommended that patients be encouraged to keep a blood glucose diary for appropriate disease management throughout the study, as well as to show the data collected to the physician / diabetes expert for evaluation. The data will not be collected by the sponsor.

Patients developing symptoms of uncontrolled diabetes mellitus and/or blood glucose levels consistently above 275 mg/dL (15.5 mmol/L), in spite of appropriate therapeutic interventions, must be discontinued from the study, as well as those patients whose HbA1c percentage is  $\geq 10\%$ , in spite of appropriate therapeutic interventions.

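### Protocol 6.4.4 applies one reduce-or-withdraw rule to all drug-related grade ≥ 3 events, laboratory changes included, while 6.4.2 exempts glucose, QTc and liver changes and sends them to different pathways in 7.5.2

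*Protocol*

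**What the plan says.** Four parts of the Protocol govern what happens after a serious tolerability problem.

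- **6.4.2, text.** In case of tolerability issues, with a pointer to Table 6-2, "the pasireotide LAR dose may be decreased to 40 mg in the next scheduled injection". Patients who cannot tolerate 40 mg, the minimum dose, are discontinued.
- **6.4.2, Table 6-2 and its note.** For a grade ≥ 3 event judged related, the action is "Decrease intramuscular pasireotide LAR dose to 40 mg". The next line reads "If the AE does not improve to grade ≤ 2 with the 40 mg dose, the patient will be withdrawn". The note adds: "The guidance above must be used for all AEs, except for changes in blood glucose and QTc and for liver safety monitoring". The three exempted types go to 7.5.2.1, 7.5.2.2 and 7.5.2.3.
- **6.4.4.** The scope is grade ≥ 3 events, including grade ≥ 3 "changes in laboratory values) that the investigator considers as directly ascribable to the study drugs". Such patients "must have their doses decreased (Section 6.4.2) or be withdrawn from the study". No exemption is stated.
- **6.4.5.1.** Adverse events, uncontrolled diabetes and clinically significant laboratory values stand on a list of reasons for which the investigator *may* withdraw a patient. The section closes by saying that the drug *must* be stopped at once if any discontinuation criterion is met, and that it may not be resumed.

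The special pathways differ from one another. For glucose (7.5.2.1): "The start or adjustment of anti-hyperglycemic treatment must be considered as soon as possible, at the discretion of the diabetes expert". No change of study-drug dose is mentioned. Discontinuation follows symptoms of uncontrolled diabetes, "blood glucose levels consistently above 275 mg/dL", or HbA1c of 10% or more, in each case despite appropriate treatment. For ALT or AST above 5 and up to 8 × ULN (7.5.2.3), the drug is interrupted and may be resumed once the value falls below 5 × ULN. For QTc (7.5.2.2), the decision on continuing refers back to 6.4.4 and 6.4.5.

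**The concern.** A site facing a drug-related grade ≥ 3 glucose or liver value can find two instructions, both in force and not the same. One is to reduce or withdraw. The other is to follow a pathway that does neither at that stage. Two sites could treat the same event differently and both claim to have followed the Protocol.

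Patient care is affected first. The analysis is also affected, because the action taken is itself data. Dose decreases are a tolerability result (Protocol 7.6 and 10.5.4; SAP 5.5.4). A comparison of response between 40 mg and 60 mg is a secondary endpoint, if applicable (Protocol 3.2.1; SAP 1.2.1). Dose reduction is a covariate in the Cox model for time to response (SAP 5.5.1 and Table 9). Reasons for ending treatment are tabulated in SAP Table 1. If the rule applied depends on the section read, these results partly describe site practice rather than the drug.

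**Working it through.** There is no plan figure to reproduce, because the point rests on the text. The table sets out what each section requires for a drug-related grade ≥ 3 event.

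| Event | 6.4.2 text, Table 6-2 and note | 6.4.4 | 7.5.2 |
|---|---|---|---|
| Ordinary event on 60 mg | Text: reduction permitted. Table: reduce; withdraw only if no improvement at 40 mg | Reduce or withdraw, with no criterion for choosing | Not applicable |
| Glucose | Exempt, go to 7.5.2.1 | Reduce or withdraw | Anti-hyperglycemic management; no dose step before the stopping values |
| Liver, ALT/AST > 5 to ≤ 8 × ULN | Exempt, go to 7.5.2.3 | Reduce or withdraw | Interrupt; may resume below 5 × ULN; discontinue if no resolution or return to baseline after 2 weeks |
| QTc | Exempt, go to 7.5.2.2 | Reduce or withdraw | Cardiology work-up, then back to 6.4.4 and 6.4.5 |
| New event arising at 40 mg | Text: discontinue if 40 mg is not tolerated. Table: not clearly covered | Only withdrawal is left, as 40 mg is the minimum | Not applicable |

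**Glucose and liver.** The second and third rows conflict. Because 6.4.4 names laboratory changes, these values cannot be read out of its scope. The glucose pathway has no reduction step. The liver pathway has interruption and resumption, which 6.4.4 does not offer.

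**QTc.** This is a loop rather than a conflict: 6.4.2 exempts QTc and points to 7.5.2.2, which points to 6.4.4, the section with the general rule.

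**Optional or mandatory.** For the ordinary event, the verb moves from *may* (6.4.2 text), to an instruction that must be used (Table 6-2 and note), to *must* with two options (6.4.4). Table 6-2 keeps withdrawal as a second step, whereas 6.4.4 allows it at once. The causality test also differs: Table 6-2 asks whether the event is related, 6.4.4 whether it is directly ascribable to the drug.

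**6.4.5.1.** A list that opens as permissive closes as mandatory. Its bar on resumption may be meant only for the liver criteria just above it, but the sentence says any criterion. A clinically significant laboratory value is on the same list, which sits badly with the resumption allowed in 7.5.2.3.

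**At 40 mg.** The second line of Table 6-2 follows the instruction to reduce, so it concerns the event that prompted the reduction. If the patient is already on 40 mg, that instruction cannot be carried out. The 6.4.2 text covers patients who do not tolerate 40 mg, but intolerance is not defined and no time is set for improvement to grade ≤ 2.

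**The case against.** The best defence is that 6.4.4 cites 6.4.2, where the exemptions stand, so the general rule should be read with the specific one. This softens the conflict without removing it. The citation is attached only to the dose-decrease option; withdrawal carries no reference. Read literally, a glucose event followed into 6.4.2 loses the decrease option, leaving withdrawal, which 7.5.2.1 does not call for until its stopping values.

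It can also be said that *may* in 6.4.2 is only permission to leave the fixed 60 mg schedule, with Table 6-2 setting when, and that 6.4.4 summarises the table's two steps. That is a fair reading and makes the verb differences the weaker part of the point. It does not explain why 6.4.4 gives no order or criterion for its two options.

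Two stronger readings are tempting and should not be made. A reader might infer that the sections contradict each other at 40 mg, with Table 6-2 keeping a patient whom 6.4.4 withdraws. Table 6-2 does not say that, and the 6.4.2 text discontinues patients who cannot tolerate 40 mg, so this is a gap. The Extension Phase rule is not in direct conflict either, since it covers recurrence after a return to 60 mg. A reader might also infer that the glucose conflict will be common because hyperglycemia is known with this drug. Protocol 1.2 reports hyperglycemia but gives no frequency of grade ≥ 3 glucose events, and describes most cases as readily controlled.

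**Conclusion.** The point stands as an inconsistency between operative sections. It is firm for glucose and liver laboratory changes, a circular reference for QTc, uneven wording for ordinary events, and a gap at 40 mg. It assumes that the glucose or liver change in question is graded 3 or higher. Protocol 7.5.1 names CTCAE version 4.0 but the documents reproduce no cut-offs, so the overlap with the 7.5.2 thresholds cannot be worked out from them.

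The size cannot be quantified. A reader might infer that each withdrawal made under 6.4.4 takes one of 19 patients (1/19 = 5.3%) out of the primary analysis. The documents do not support that:

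- Patients who stop early still attend Visit 10, 28 ± 3 days after the last dose, with all its evaluations (6.4.4), and MRI is among them. Whether such a scan counts as Week 24 is not stated.
- 23 patients are enrolled to obtain 19, so 23 − 19 = 4 losses are already allowed for (10.6).
- A last-observation-carried-forward sensitivity analysis covers missing Week 24 values (10.4.4).

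The effect that can be claimed is on consistency of care and on the meaning of the dose-reduction, withdrawal and dose-related results. That is enough to call for correction, but it does not undermine the primary analysis.

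**What to change.** Reconcile Protocol 6.4.2, Table 6-2, 6.4.4, 6.4.5.1 and 7.5.2.1 to 7.5.2.3 so that each type of event has one stated scope, one exemption list, one causality criterion and one action wherever it appears. State whether each action is optional or mandatory, and cover the patient already on 40 mg. Break the QTc loop by stating which criteria decide continuation. Make clear which items in 6.4.5.1 the closing stop and no-resumption sentences govern. Which action applies in each case is the sponsor's clinical decision, and nothing here favours one section over another.

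The cost is amendment wording, with the usual approvals and site notification. No visit, assessment or sample-size change is needed. If patients have already been treated under the present text, the report should say which rule was applied to each dose reduction and withdrawal.
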